NCT#: NCT04138017

Document Date: 19 August 2021

PROTOCOL

Background

1. Provide the scientific background, rationale and relevance of this project.

INSTRUCTIONS

- This should include a referenced systematic evidenced-based review when possible.
- If this study involves qualitative research explain the major constructs of your study.
- Do not state in this section what you plan to do in this study. This information should be entered later under "What will be done in this protocol?"
- Do not include the bibliography in this section.
- For studies submitted under the Expedited review criteria, this section need not be more than a few paragraphs.
- For those studies where data will be analyzed collaboratively by multiple sites doing
 a similar study for which there is no common protocol (Collaborative Site Analysis
 Study) include a description of the common scientific goals/ procedures/data points.
- If this is a FIVE YEAR UPDATE make sure the information throughout the protocol includes the most current information.

Answer/Response: Arthrodesis procedures for the ankle and hindfoot are performed to correct deformity and treat end-stage arthritis. However, recent literature has demonstrated that 10-40% of ankle fusions result in non-union (1,2). For triple arthrodesis (talonavicular, subtalar, and calcaneocuboid joints), published rates of non-union range from 0-10% (3). However, recent literature from our institution demonstrated significantly higher rates of non-union when calcaneo-cuboid sparing hindfoot arthrodesis was performed (4). Given that not every non-union results in a revision surgery, it is likely that the published rates of non-union underestimate the true rate of this complication. Due to the extended period of convalescence after these major arthrodesis procedures, non-union is a devastating outcome. Loss of mobility, loss of income from employment, and increased health care expense and patient risk for a second procedure contribute to the economic and emotional impact of non-union upon these patients.

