If this study involves biomedical research clearly state the objectives and hypotheses and clearly define the primary and any secondary outcome measures. If this study involves qualitative research clearly state your research hypothesis or question.

This section should not include information already included in other sections such as background information or information from the procedures section.

Answer/Response: To evaluate 1-Year implant survivorship in subjects who receive the implant when used for primary ankle or hindfoot arthrodesis procedures.

Study Design: Biomedical

1. Will controls be used?

Answer/Response: No.

► IF YES, explain the kind of controls to be used.

Answer/Response:

2. What is the study design?

Example: case series, case control study, cohort study, randomized control study, single-blind, double-blind, met-analysis, systematic reviews, other. You may also view the IRB-HSR Learning Shot on this topic to help you answer this question. (http://www.virginia.edu/vpr/irb/learningshots/Writing protocol June09/player.html

Answer/Response: This is a post-market, prospective, non-randomized, PI initiated, open-label clinical evaluation of the implant for use in primary ankle or hindfoot

Version Date: 08/19/2021 Page Number: 2 of 10

arthrodesis. Data will be collected at specific time points and entered into case report forms (CRFs) based on the information contained in the patient medical records.

3. Does the study involve a placebo?

Answer/Response: No.

▶ IF YES, provide a justification for the use of a placebo

Answer/Response:

Human Participants

 Ages:
 18-80

 Sex:
 All

 Race:
 All

Subjects- see below

INSTRUCTIONS: For question 1-4 below insert an exact #. Ranges or OPEN is not allowed. This # should be the maximum # you expect to need to enroll (i.e. sign consent) If you are only collecting specimens the number of participants should equate to the # of specimens you need. If you are collecting only data from a chart review the number should designate the number of subjects whose medical records you plan to review. Age/ Sex/Race criteria should designate the demographics of participants from whom you will obtain the specimen/data.

1. Provide target # of subjects (at all sites) needed to complete protocol.

INSTRUCTIONS: If this is NOT a database protocol, this number should be the same as the number of subjects needed to obtain statistically significant results.

Answer/Response: 15

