2. Describe expected rate of screen failure/ dropouts/withdrawals from all sites.

Answer/Response: 10%.

3. How many subjects will be enrolled at all sites?

INSTRUCTIONS: This number must be the same or higher than the # from question # 1 in order to account for the # of screen failures, dropouts, withdrawals described in question # 2.

Answer/Response: 18.

4. How many subjects will sign a consent form under this UVa protocol?

INSTRUCTIONS: If the protocol does not have a consent form- the number listed here should reflect such things as the number of subjects from whom specimens will be obtained, the number of charts to be reviewed etc.

Answer/Response: 18.

Version Date: 08/19/2021 Page Number: 3 of 10

Inclusion/Exclusion Criteria

INSTRUCTIONS:

- The inclusion and exclusion criteria should be written in bullet format.
- This item applicable if the study will require consent (verbal or written). Unless there is a scientific reason for not recruiting a certain type of vulnerable population(e.g. not enrolling fetuses, neonates or children in a study regarding Alzheimer's) list the following vulnerable populations under either Inclusion or Exclusion criteria below: pregnant women, fetuses, neonates, children, prisoners, cognitively impaired, educational or economically disadvantage, non- English speaking subjects.
- If you will not enroll subjects who do not speak English because certain procedures cannot be carried out if the subject does not speak English (e.g. a survey is not validated in other languages) insert the following as an Inclusion Criteria: Willingness and ability to comply with scheduled visits and study procedures.
- If this is a collection of only retrospective* specimens or data, the inclusion criteria must include a start and stop date for when specimens/ data will be collected.
- The stop date must be prior to the version date of this protocol.
- *Retrospective: all specimens are in a lab at the time this protocol is approved by the IRB. All data exists in medical records or records from previous studies at the time this protocol is approved by the IRB.

1. List the criteria for inclusion

Answer/Response:

- Patient with prescribed standard of care unilateral hindfoot ankle arthrodesis
 procedure who will receive the ViviGen® Cellular Bone Matrix as part of their clinical
 care
- Age 18-80
- Willing to complete all follow up evaluations

2. List the criteria for exclusion

Answer/Response:

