- --Recap of study objectives and endpoint definitions. An assessment of how study objectives will be assessed by identifying & defining which endpoints will be used to assess each component of the study objectives.
- --The study design should include contingencies for early stopping, interim analyses, stratification factors (If applicable), and any characteristics to be incorporated in analyses.
- --The power/precision of the study to address the major study endpoint(s), the assumptions involved in the determination of power/precision.
- --If statistical hypothesis testing is included then specify the null and alternative hypotheses, the test statistic, and the type I and II error rates
- --If precision of an estimate, then provide a definition for precision
- --If other, then specify

Answer/Response: We will compare primary outcome measures as a binary outcome using chisquare or Fisher exact analyses using existing failure rates as a historical control. We will use standard parametric statistical analyses to determine change from pre-post surgery and referencing historical control data obtained from the literature. Multivariate statistical modelling will be considered for potential sources of confound if appropriate.

3. Provide a justification for the sample size used in this protocol.

Include the anticipated accrual rate, the accrual goal for the study, including accrual goals by strata if appropriate, adjustments for drop-outs etc. and study duration.

Answer/Response: ViviGen is already an FDA approved biologic, therefore a large sample size is not needed.

4. What is your plan for primary variable analysis?

Include a sketch of the analysis to assess primary study objectives.

Answer/Response: Radiographic evidence of successful arthrodesis confirmed on CT (defined by >50% fusion)

5. What is your plan for secondary variable analysis?

Include the following:

- -- A sketch of the analysis to assess secondary study objectives.
- --For phase III studies, the power/precision of the study to address the secondary objective(s).

Answer/Response:

- Clinical & Radiographic evidence of failure (obvious non-union or hardware failure)
- Patient reported outcomes scores
- Vitamin D levels

6. Have you been working with a statistician in designing this protocol?

Answer/Response: No.

IF YES, what is their name?

Answer/Response:

Version Date: 08/19/2021 Page Number: 6 of 10

7. Will data from multiple sites be combined during analysis?

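### Multivariable modelling, the plan's only analytic remedy for confounding, cannot adjust the comparison with historical failure rates, and procedure mix is left unhandled

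*Combined protocol and SAP*

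**What the plan says.** The study has no controls (Study Design, question 1), and everyone who meets the inclusion criteria receives the graft as part of clinical care. Statistical Considerations, question 2, compares the binary primary outcome with existing failure rates by chi-square or Fisher exact test. It then plans parametric pre-post analyses, "referencing historical control data obtained from the literature", and closes with the only sentence on confounding: "Multivariate statistical modelling will be considered for potential sources of confound if appropriate". It names no covariate, model, outcome or criterion for when modelling would be appropriate. Question 4 of the same section defines success as more than 50% fusion on CT.

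The Background pools four procedures (ankle, tibiotalocalcaneal, subtalar and triple arthrodesis) and gives numeric non-union rates for two of them: "recent literature has demonstrated that 10-40% of ankle fusions result in non-union", and "For triple arthrodesis (talonavicular, subtalar, and calcaneocuboid joints), published rates of non-union range from 0-10" per cent. No procedure split is planned, and there is no stratification. Under Human Participants, the target number is "Answer/Response: 15" and the number enrolled is "Answer/Response: 18".

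**The concern.** A regression can adjust a treatment comparison only if both treatments, with their covariates, are in the data. Here one side is a cohort in which all subjects are treated, and the other is a rate taken from publications. Whatever the model estimates, it is not the difference between graft and historical control.

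The factor that most visibly differs between this cohort and any single benchmark is the procedure performed. The Background rates for ankle and triple fusions meet only at 10%, so the rate to expect without any graft effect depends on who happens to enrol. If that is not handled, the same observed result can look ordinary or look like superiority. A model fitted to a handful of failures could also be reported as an adjusted result when it has adjusted nothing in the comparison that matters.

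**Working it through.** **The plan's own figure.** Target 15 and expected loss "Answer/Response: 10" per cent give 15 / (1 − 0.10) = 16.7, rounded up to 17. The stated 18 is close to this and slightly generous. The target of 15 itself has no calculation behind it, and no expected number of failures is stated.

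**Expected failures in 15 subjects** (N × rate, Background rates):
- triple: 15 × 0 = 0 to 15 × 0.10 = 1.5
- ankle: 15 × 0.10 = 1.5 to 15 × 0.40 = 6.0

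A mixed cohort therefore lies between 0 and 6. If all 18 were analysed, the top would be 18 × 0.40 = 7.2. The CT-confirmed fusion rates of 84% and 65% in the cited growth-factor trial mean non-fusion of 16% and 35%, or 2.4 and 5.25 failures in 15.

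**Can a model of failure be fitted?** The documents give no split, so two splits are assumed for illustration. A group with no failures, or with only failures, gives an infinite coefficient. The chance that at least one group is like this is 1 − Π[1 − (1 − p)^n − p^n]. For groups of 7 and 8 at p = 0.10, this is 1 − (1 − 0.478)(1 − 0.430) = 0.70.

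| Failure rate | One binary covariate (7/8) | Four procedures (4/4/4/3) |
|---|---|---|
| 10% | 70% | 99% |
| 16% | 47% | 95% |
| 35% | 8% | 64% |
| 40% | 5% | 57% |

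**Effect of procedure mix.** Only ankle and triple have numeric rates, so these two alone are used. Weighted rate = (n_ankle × p_ankle + n_triple × p_triple) / 15.

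| Ankle / triple | Low ends (10%, 0%) | High ends (40%, 10%) |
|---|---|---|
| 3 / 12 | 0.3 / 15 = 2% | (1.2 + 1.2) / 15 = 16% |
| 12 / 3 | 1.2 / 15 = 8% | (4.8 + 0.3) / 15 = 34% |

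**What the mix does to one result.** Take 1 failure in 15 at the high-end rates, and sum the exact probabilities of 0 and 1 failures.
- 3 ankle, 12 triple: P(0) = 0.6³ × 0.9¹² = 0.061. P(1) = 3 × 0.4 × 0.6² × 0.9¹² + 0.6³ × 12 × 0.1 × 0.9¹¹ = 0.122 + 0.081 = 0.203. Total 0.26.
- 12 ankle, 3 triple: P(0) = 0.6¹² × 0.9³ = 0.0016. P(1) = 12 × 0.4 × 0.6¹¹ × 0.9³ + 0.6¹² × 3 × 0.1 × 0.9² = 0.0127 + 0.0005 = 0.0132. Total 0.015.

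**What weighting does not change.** With 0 failures in 15, the one-sided P is 0.90¹⁵ = 0.21 against 10% and 0.84¹⁵ = 0.073 against 16%. Under the 3/12 mix at high-end rates, it is the 0.061 above.

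**The case against.** The modelling sentence is conditional and commits to no specification, so the four-group split is illustrative only. With one binary covariate and a failure rate of 35 to 40%, separation is uncommon (8% and 5%). A reader might infer that no model of failure could ever be fitted; these figures do not support that. They show low precision throughout and frequent breakdown at the lower rates. The objection leaves the main argument untouched, because a lack of treatment contrast is not cured by a model that converges.

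A reader might infer that the plan controls confounding in no other way. It does so by design: the exclusions cover nicotine use, BMI above 40, A1C above 8.0, vitamin D below 30 ng/mL, prior infection and large bone defects. These do not balance procedures, and they may make the cohort lower-risk than the published series.

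A reader might also infer that all multivariable modelling should go. The sentence directly follows the pre-post analyses, and the failure count says nothing against a small model of continuous scores.

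The strongest objection is to the remedy. The Background rates are published non-union rates, which the protocol itself thinks are probably too low, whereas the endpoint is CT fusion above 50%. The CT-based rates it cites are not given by procedure. Weighting could therefore remove case-mix bias and leave bias from the endpoint definition. That stands as a limitation to state; an unweighted benchmark has the same defect and ignores case mix as well.

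**Conclusion.** The point holds for the binary failure comparison. The planned modelling cannot adjust it at any sample size, and about 0 to 6 expected failures make such a model unreliable in any case. Procedure mix alone can move the benchmark from 16% to 34% at the top of the published ranges, or from 2% to 8% at the low ends. It can move the lower-tail probability of a 1/15 result from 0.26 to 0.015.

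This rests on three assumptions: that 15 subjects are analysed; that only the two procedures with numeric rates are enrolled, in the illustrative mixes shown; and that the historical data are published rates. The Background does cite a series from the sponsor's own institution, but the plan names no patient-level dataset.

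A reader might infer that a weighted benchmark makes the historical comparison sound. It does not: it corrects procedure mix and leaves patient risk, endpoint definition and precision as they were. The change should be made, because the comparison can mislead without it.

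**What to change.** In Statistical Considerations, question 2:

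1. State that no multivariable model will be used to adjust the binary failure comparison with historical rates. Models of continuous scores are unaffected.
2. Pre-specify a historical failure rate, with its source, for each of the four procedures, CT-based where available.
3. Lead with the observed failure proportion and its exact 95% CI, and list results by procedure descriptively.
4. Compare observed failures with the expected total, Σ (subjects having the procedure × its historical rate), using the exact distribution of a sum of binomials with unequal probabilities. For this comparison, that takes the place of the chi-square or Fisher test.
5. Repeat at the low and high ends of each published range. Where a low end is 0%, as for triple, show the expected count without a test, since a single failure would be impossible under that benchmark.
6. State as limitations that weighting corrects procedure mix only, not patient risk or the difference between CT fusion above 50% and published non-union, and that it does not improve precision.

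The cost is protocol wording and a short calculation from surgical information already recorded at Visit 2. The real work is finding subtalar and tibiotalocalcaneal rates, which the documents do not give, and fixing all four rates before outcomes are known.

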Currently, many alternatives to autograft harvest are being evaluated for foot and ankle arthrodesis. Given the known complications of autograft harvest (incision pain, nerve injury, infection, 1), alternatives which possess osteogenic, osteoconductive, and osteoinductive properties are an attractive option when supplementing complex hindfoot arthrodesis procedures. A recent publication demonstrated a superior fusion rate for purified recombinant human platelet-derived growth factor BB homodimer (rhPDGF-BB) when compared to autograft (5). However, arthrodesis rates, as confirmed on CT scan, were only 84% and 65% respectively.

ViviGen (Depuy Synthes) is a cellular bone matrix, which includes viable osteoblasts within a corticocancellous and demineralized bone carrier, represents a unique alternative to autograft or existing products which utilize mesenchymal stem cells. ViviGen Cellular Bone Matrix is a Human Cells, Tissues, and Cellular and Tissue-based Product (HCT/P) as defined by the U.S.

Version Date: 08/19/2021 Page Number: 1 of 10

Food and Drug Administration in 21 CFR 1271.3(d). ViviGen Cellular Bone Matrix is processed from donated human tissue, resulting from the generous gift of an individual or his/her family. This product is classified as a **biologic** by the FDA. Given our encouraging early data using Vivigen for complex and revision arthrodesis procedures in the foot and ankle, our Foot and Ankle Clinical research group at the University of Virginia wishes to conduct a prospective study to evaluate 1-Year implant survivorship in subjects who receive the implant when used for primary ankle or hindfoot arthrodesis procedures as part of their clinical care.

Our study would prospectively follow primary ankle or hindfoot arthrodesis procedures. Ankle arthrodesis, tibiotalocalcaneal arthrodesis, subtalar and triple arthrodesis procedures would be included in this cohort, and CT scan would be utilized to demonstrate successful arthrodesis (defined by >50% fusion). Patient outcome measures including Foot and Ankle Activity Measures, AOFAS hindfoot score, and VAS pain scores would be recorded pre-operatively and for 1 year post operatively.

The purpose of this study is to examine 1-year outcomes. ViviGen Cellular Bone Matrix is being given as part of clinical care. The only research procedures are questionnaires and blood draw for Vitamin D.

Objectives/Hypothesis

INSTRUCTIONS:

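### The target of 15 has no power or precision basis, and the planned test against historical failure rates names no comparator, alpha or sidedness, so a comparator picked later could decide the conclusion

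*Combined protocol and SAP*

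**What the plan says.** All places are in the combined protocol and SAP.

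- **Human Participants, questions 1 to 4.** The target is 15, with 10% loss expected and 18 to be enrolled. The form's instruction for the target is that "this number should be the same as the number of subjects needed to obtain statistically significant results".
- **Statistical Considerations, question 3.** The whole justification is: "ViviGen is already an FDA approved biologic, therefore a large sample size is not needed".
- **Statistical Considerations, question 2.** The binary primary outcome is to be compared by chi-square or Fisher exact methods "using existing failure rates as a historical control". Where a test is planned, the form asks the author to "specify the null and alternative hypotheses, the test statistic, and the type I and II error rates", and it asks for power or precision in any case. The answer gives none of these.
- **Statistical Considerations, question 4.** The primary variable is fusion above 50% on CT. No visit is named. Study Procedures lists CT at 3, 6 and 12 months.
- **Background.** It reports that "10-40% of ankle fusions result in non-union", that is 60% to 90% fused. It gives 0-10% non-union for triple arthrodesis (90% to 100% fused), and CT-confirmed fusion of 84% for a growth-factor product and 65% for autograft. None is chosen as the comparator.
- **Objectives/Hypothesis and Study Design.** The objective is "To evaluate 1-Year implant survivorship in subjects who receive the implant". There are no controls and no superiority hypothesis. The Background adds: "The purpose of this study is to examine 1-year outcomes".

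**The concern.** Approval status says nothing about how precisely 15 patients estimate a fusion rate, or what difference they could detect. The form treats the target as the number needed for significance, so a reader will assume that some calculation lies behind it.

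The larger problem is the undefined test. The candidate rates in the Background are far apart. If the same data beat one of them and not another, and the comparator is not fixed beforehand, whoever picks it later also picks the conclusion. The unnamed test and sidedness add further freedom.

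**Working it through.** **Inputs.** n = 15, 18 enrolled and 10% loss (Human Participants). Candidate fusion rates of 65% and 84% (CT-confirmed, Background) and 90% (the 10% non-union bound shared by the ankle and triple ranges). Assumptions made here because the protocol states none: one-sample exact binomial test, two-sided 0.05, p-value equal to the sum of the probabilities of all outcomes no more likely than the one observed.

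**The plan's own figures.** The 15 cannot be reproduced, as there is no null rate, alternative, alpha, power or precision target. Only the loss allowance can be checked: 15 / 0.90 = 16.7, so 17, against the stated 18. That is close enough and is not an issue.

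**All 15 fused.**
- Against 65%: 0.65^15 = 0.0016; lower outcomes (3 or fewer) add 0.0005; p = 0.002.
- Against 84%: 0.84^15 = 0.0731; lower outcomes (10 or fewer) add 0.0778; p = 0.15.
- Against 90%: 0.90^15 = 0.2059; lower outcomes (12 or fewer) add 0.1841; p = 0.39.

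**14 of 15 fused.**
- Against 65%: upper tail 0.0142; 5 or fewer add 0.0124; p = 0.027.
- Against 84%: upper tail 0.2821; 11 or fewer add 0.2092; p = 0.49.

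Against 65%, 13 of 15 gives p = 0.10, so 14 of 15 is the cut-off.

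**Sensitivity to what is not stated.**
- One-sided uncorrected chi-square, 15 of 15 against 84%: z = 0.16 / sqrt(0.84 × 0.16 / 15) = 1.69, p = 0.0455. The two-sided value is 0.091.
- Two-sample Fisher, 14 of 15 against 65% with an assumed historical group of 20 (13 of 20 fused): p = 0.10. The documents give no historical n.

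**Power against 65%.**
- 15 evaluable, 14 needed. P(X ≥ 14) = 15·p^14·(1 − p) + p^15 = 28%, 55% and 83% at p = 0.84, 0.90 and 0.95.
- 16 evaluable (18 × 0.90 = 16.2). 14 of 16 has upper tail 0.045 and fails two-sided, so 15 are needed. 16·p^15·(1 − p) + p^16 = 25%, 51% and 81%.

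**Precision with 15.** The expected width of the exact (Clopper-Pearson) 95% interval is 49, 39 and 34 percentage points at true fusion of 65%, 84% and 90%. The lower limit is 68.1% for 14 of 15 and 78.2% for 15 of 15.

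**The case against.** *A small post-market, single-arm study needs no power calculation, and comparison with a historical rate is legitimate.* Both are true. A descriptive study can rest on precision, and a single-arm test is sound if it is fully specified beforehand. What stands is that the plan gives no precision either, and includes a test that it does not specify.

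*The contrast depends on an assumed two-sided 0.05.* Correct. A reader might infer that no test on 15 patients could ever beat 84%. The documents do not support that, because they fix neither test nor sidedness, and a one-sided chi-square on a perfect result just crosses 0.05. That the answer moves with an unstated choice is part of the concern.

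*An interval does not remove the comparator problem.* Largely right. The Clopper-Pearson interval inverts the doubled-tail exact test, so setting its lower limit beside a rate picked later is the same test under another name. This is why the historical rates to be displayed must all be listed in advance.

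*CT fusion is not the stated objective.* Also right. The documents never define implant survivorship as CT fusion, and clinical or hardware failure is listed separately as secondary. The estimate proposed below addresses the question 4 endpoint only.

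A reader might also extend the point to the second sentence of the question 2 answer, on pre-post change "referencing historical control data obtained from the literature". That sentence does not plainly commit to a test, and nothing computed here bears on those outcomes, so it is left alone.

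**Conclusion.** The concern holds. The target of 15 has no statistical basis in the documents, and the primary comparison lacks a comparator, alpha and sidedness. Under the assumed one-sample exact test at two-sided 0.05, a perfect result is significant against one CT-confirmed rate in the Background (65%, p = 0.002) and not against the other (84%, p = 0.15). A result with one non-union behaves the same way (p = 0.027 and 0.49). The two-sample p-value rests on an assumed historical group of 20, and the 16-evaluable case takes the stated 10% loss at face value.

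A reader might infer that 15 patients are too few and enrolment must rise. The documents do not support that: the objective is descriptive and carries no superiority hypothesis. The data remain usable; it is the inference as written that is undefined.

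**What to change.** No change in enrolment.

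1. Replace the question 3 answer with:

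> Fifteen evaluable subjects allow estimation of the CT fusion rate with an exact 95% CI about 39 percentage points wide on average if the true rate is 84% (a planning assumption; about 49 points at 65% and 34 at 90%). The study is not sized to show superiority over historical rates and no such claim will be made.

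2. Replace the first sentence of the question 2 answer with:

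> The primary analysis is the proportion of subjects with CT-confirmed fusion (>50%) at the 12-month visit, with its exact (Clopper-Pearson) 95% CI. The historical rates cited in the Background (CT fusion 65% and 84%; ankle non-union 10-40%; triple arthrodesis non-union 0-10%) will all be shown beside it for description only.

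Twelve months is suggested because the objective is a 1-year one. The investigator may name the 3- or 6-month CT instead, before the data are seen.

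If a test is kept, question 2 must name one comparator rate, a one-sample exact test, alpha and sidedness in advance, and question 3 must state its power.

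**Cost.** Wording in two answers, with no added patients or procedures. The stated ambition becomes less favourable and a formal test against 60-65% is given up, although the lower confidence limit still shows whether those rates are excluded.

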VISITS 5, 6, and 7 –3 months, 6 months and 12 months Post-Surgery

The following procedures will be done as **part of your clinical care.** The results will be recorded for research purposes:

- Physical assessment of hindfoot/ankle, including vital signs
- X-rays of the hindfoot/ankle

The following procedures/assessment will be done solely for research purposes:

- Questionnaires
- Blood draw (1 ½ teaspoons) and analysis for Vitamin D levels (only at the 6 month visit)
- CT scan of your ankle/hindfoot
- At the conclusion of Visit #7, participation in the study is complete.
- 2. If this protocol involves study treatment, explain how a subject will be transitioned from study treatment when they have completed their participation in the study.

Example: If the subject will be taking an investigational drug, will they need to be put back on an approved drug when they have completed the study? If yes, explain how this will be accomplished and who will cover the cost. If the subject has a device implanted will it be removed? Again- who will cover the cost of the removal? **Instructions:** Answer NA if this study does not involve a study treatment.

Answer/Response: N/A.

Subject Compliance with Study Procedures

1. **Explain how the study team will monitor the subject for compliance with the study procedures.** (e.g. study team will administer study drug/ study interventions, study drug inventory of dispensed and returned drug, diary etc.)

Answer/Response: Study visits coincide with standard of care follow-up visits to their surgical procedure.

2. **Describe criteria for when a subject is considered to be non-compliant with study procedures.** (e.g. subject returns more than 20% of the study drug, subject misses 20% of study visits)

Answer/Response: Subject misses 30% of study visits

Bibliography

Version Date: 08/19/2021 Page Number: 9 of 10

- 3. K.L. Wapner. Triple arthrodesis in adults. J Am Acad Orthop Surg, 6 (1998), pp. 188–196

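### The primary outcome is a >50% CT fusion call in an open-label, single-arm study compared with historical rates, and the plan specifies no masked reading

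*Combined protocol and SAP*

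**What the plan says.** Statistical Considerations, item 4, gives the whole plan for the primary variable: "Radiographic evidence of successful arthrodesis confirmed on CT (defined by >50% fusion". Item 2 of that section says the primary outcome is binary and will be compared, by chi-square or Fisher exact test, with failure rates that already exist. It does not say which rate, and it gives no significance level or success rule.

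Study Design, question 1, says there are no controls. Question 2 describes a "prospective, non-randomized, PI initiated, open-label clinical evaluation of the implant" and says the case report forms are completed "based on the information contained in the patient medical records".

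Study Procedures lists, for Visits 5, 6 and 7 (3, 6 and 12 months), a physical assessment, X-rays, questionnaires and "CT scan of your ankle/hindfoot". None of the three CTs is named as the primary one.

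The Background states the group's prior experience: "Given our encouraging early data using Vivigen for complex and revision arthrodesis procedures in the foot and ankle".

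The documents do not say who reads the CTs, how percent fusion is measured, whether the reader is masked to anything, or whether there is a second reader.

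**The concern.** In a controlled trial with masked reading, a lenient reader is lenient to both arms and much of the error cancels. Here there is one arm, and the comparison is with rates that other readers produced elsewhere. Any systematic leniency stays in the difference.

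The only route the plan describes for a CT result is the medical record, and each scan belongs to a visit with an examination and questionnaires. As written, the scans may be read in sequence by someone who knows how long ago the operation was and how the patient is doing. Treatment cannot be masked, because every patient receives the graft. Visit order and clinical course can be.

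At stake is the one result the study is built to report. With about 15 patients, each call carries a lot of weight.

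**Working it through.** **Inputs from the documents**
- Target 15, expected loss 10%, enrolled 18 (Human Participants, items 1 to 3).
- CT-confirmed fusion rates of 84% for the growth factor and 65% for autograft (Background).
- Ankle non-union of 10-40%, so fusion of 60-90%; triple arthrodesis non-union of 0-10%, so fusion of 90-100% (Background).
- CT at three visits.

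**Assumptions:** exact one-sample binomial test, significance level 0.05 two-sided. The plan gives neither a level nor a benchmark.

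**The plan's own figure.** 15 / (1 - 0.10) = 16.7, which rounds up to 17. The stated 18 is one more, so enrolment covers the expected loss. The target of 15 cannot be reproduced, because no error rates or fusion rates are given for it.

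**Weight of one call.** 1/15 = 6.7 points; 1/18 = 5.6 points.

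**Effect of one call on the test.** The two-sided p is the total probability, under the benchmark rate, of every count no more likely than the one observed. For 14/15 against 65%, the upper tail P(X≥14) = 0.0142 and the matching lower tail P(X≤5) = 0.0124, which sum to 0.027.

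| n | Benchmark | Lower count | p | One more fused | p |
|---|---|---|---|---|---|
| 15 | 65% | 13 | 0.104 | 14 | 0.027 |
| 15 | 60% | 12 | 0.186 | 13 | 0.036 |
| 18 | 65% | 15 | 0.138 | 16 | 0.045 |

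At n=15 against the higher benchmarks, even the best possible count falls short. For 15/15 against 84%, one-sided p = 0.84^15 = 0.073 (two-sided 0.151). Against 90%, one-sided p = 0.90^15 = 0.206 (two-sided 0.390). No count is significant in the graft's favour, so one upgraded call cannot create a positive finding there. At n=18 against 84%, 18/18 gives one-sided 0.043 but two-sided 0.098.

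**Check with the plan's named tests, n=15 against 65%.** One-sample chi-square gives 0.079 for 13/15 and 0.021 for 14/15. Fisher exact against an assumed historical sample of 50 to 400 gives 0.097-0.138 and 0.024-0.049. The pattern is the same.

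**How often one upgrade could matter, against 65%.** A correct reading would have to give exactly 13 of 15: P = 105 × q^13 × (1-q)^2, where q is the true fusion rate. With q assumed to be 84% this is 0.28, and with 90% it is 0.27. These are ceilings, since one of the two scans not fused must also be near the threshold and be called up.

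**Reading load.** 18 subjects × 3 CTs = 54 scans at most.

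**The case against.** The strongest reply is that the arithmetic does not measure the defect. That one call among 15 can cross 0.05 follows from a small sample and a binary outcome, and would be just as true with perfectly masked readers. This stands. The documents give no frequency of borderline scans and no reading error rate, so the size of any bias cannot be computed. The figures show only how little error would be needed.

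Four stronger readings are tempting, and the documents do not support them.
- A reader might infer that the CTs are read by someone who knows the patient. The plan is silent on the reader. It fails to exclude this, and no more can be said.
- A reader might infer that one borderline scan decides the result. That holds against benchmarks of 60-65%. It does not hold at n=15 against 84% or 90%, and the plan names no benchmark.
- A reader might infer that the error is known to favour the product. That direction is a reasonable expectation in an open-label study by a group with encouraging experience, but it remains an assumption.
- A reader might infer that masking is the only protection available. A written measurement rule, a fixed visit, a rule for operations that fuse several joints, or a second reader with adjudication would each help.

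It can also be said that the missing benchmark, primary visit and success rule come first. They are serious gaps, but they do not close this one: a fully specified test of an unmasked reading would still carry it.

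**Conclusion.** The point holds in limited form. The plan rests its primary outcome on a threshold reading in an open-label, single-arm study and says nothing that would keep knowledge of the visit or clinical course from the reader. Leniency, if it occurs, has no concurrent arm to absorb it.

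The firm part of the size is the 6.7 points per call at n=15. The change from non-significant to significant is an illustration that depends on a benchmark of 60-65%, a two-sided 0.05 level and an exact test, none of which the plan states. The amount and direction of reading bias are not shown by the documents. This is a weakness that should be repaired by a change of text. It is not evidence that any reading has been or will be wrong.

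**What to change.** Add to Statistical Considerations, item 4:
- The >50% call that sets the primary variable is made in one batch after the last 12-month CT, by the person already reading the study CTs. If the existing readers include one who is not the treating surgeon, that reader is preferred.
- Scans are coded and placed in random order across subjects and visits (at most 54).
- The reader has no access to questionnaires, visit date, clinical notes or revision status.
- Calls are locked before they are merged with the clinical data.
- The 12-month CT is the primary reading, to match the 1-year objective.
- Any clinical reads continue unchanged for care but do not set the primary variable.

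In the same edit, reconcile the Background, which limits research procedures to questionnaires and a vitamin D blood draw, with Study Procedures, which lists the CT as done solely for research. This bears on whether a separate research reading exists at all.

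**Cost.** One batch reading of existing scans, plus coding by study staff, with no added scan, visit or patient. That no added reader is needed assumes a reader is already in place, since the documents name none. The primary result waits for the last scan. In so small a sample, a reader who saw the scans clinically may recognise some of them, so masking is partial and should be reported as such. The change does not settle how percent fusion is measured or how several joints are combined; those need their own rule.
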